Nutrition as a risk factor and predictor of the outcome of orthobiological treatments for

knee osteoarthritis

PI: [name]

Laboratorio di Biotecnologie Applicate all'Ortopedia Istituto Ortopedico Galeazzi [name]

SYNOPSIS

Title	Nutrition as a risk factor and predictor of the outcome of orthobiological treatments for knee osteoarthritis					
Protocol number	Nutririsk(L4154)					
Type of study	Monocentric, observational with additional procedure (extra routine blood sampling, questionnaires and measurement of Nutritional status), prospective, non-controlled.					
Duration	36 months					
PI	[name]					
General Aim	The general purpose of this study is to evaluate the relation between the nutritional status of patients, the features of the orthobiologics products used for patients' treatment and the clinical outcomes after one-step conservative regenerative treatment for knee osteoarthritis.					
Primary Outcome:	The primary outcome of the study will be the identification of the proportion responders and non-responders patients to the orthobiologic treatment (according OMERACT-OARSI [1] criteria) at 6-month follow-up and of their related nutrition status.					
Secondary Outcomes	 The secondary outcomes of the study will be: the identification of the proportion of responders and non-responders patients to the orthobiologic treatment (according to OMERACT-OARSI criteria [1]) at 2 and 12-month follow-up and of their related nutritional status; the characterization of the orthobiologic products used for the patient's treatment. 					
Patient enrolment	 Patients affected by knee osteoarthritis undergoing conservative regenerative medicine procedures with autologous material at IRCCS Istituto Ortopedico Galeazzi and participating to the observational study "REGAIN" will be enrolled for this study: 88 patients will be needed: 22 subjects with body mass index (BMI) considered normal weight (≥18.5 and ≤25) undergo to Platelet-Rich Plasma (PRP) treatment; 22 subjects with BMI values that exceed the normal weight range (BMI>25) undergo to PRP treatment; 22 subjects with BMI within the considered normal weight range (≥18.5 e ≤25) and undergo to microfragmented adipose tissue treatment; 22 subjects with BMI values that exceed the normal weight range (≥18.5 e ≤25) and undergo to microfragmented adipose tissue treatment; 					

1.0 Background

Osteoarthritis (OA) is a multifactorial pathology that includes the synovial fluid inflammation and damage to the articular cartilage with consequent loss of it and remodeling of the subchondral bone [2]. Obesity, metabolic syndrome and diabetes can directly influence the development of OA [3]. To date, the main treatments of this disease concern the control of symptoms or, in the most severe cases, the replacement of the joint [4-5]. Although the Osteoarthritis Research Society International guidelines recommend physical exercise and weight loss in overweight and obese subjects, this type of solution is often not implemented [6]. Obesity and therefore the high body mass index (BMI), represent a risk factor for OA not only for the high load that the joint has to bear, but also for the inflammatory state, albeit mild, deriving from it at systemic level, as demonstrated by the presence of OA in obese patient hands [7]. Besides to the fact that the high BMI leads to an increase in the OA incidence, it is interesting to investigate the role of an incorrect and inadequate nutritional status in the arthrosis pathology, with particular attention to the level of the quality of the patient's autologous product (orthobiologic) uses for the treatment. Orthobiologic is a promising nonoperative treatment defined as biological material (including platelet rich plasma (PRP), mesenchymal stem cells, microfragmented adipose tissue) used to improve the healing of a musculoskeletal tissue such as cartilage. They promote healing process through the release of growth factors and molecules involved in healing and inflammation [8].

It is easy to understand how the success of a treatment depends on the quality of the product used and it becomes essential to find strategies capable of improving the quality of starting material especially in terms of antiinflammatory and immunomodulatory potential. It is known that diet directly influences the inflammatory state both at the systemic level and at the joint tissue level. Just as an incorrect diet causes an increase in the inflammatory state [9], a balanced and controlled diet can modulate the structure of cytokines favoring the anti-inflammatory ones as already demonstrated [10]. In this contest, a clear example is represented by Mediterranean diet, resulted associated with lower prevalence of OA [11]. Between the conservative treatment for OA, PRP [12] and Microfragmented adipose tissue [13] injection represent innovative regenerative approaches more and more widespread. Previous study demonstrated that dietary can induced changes in fatty acid composition of human plasma, platelet, and erythrocyte lipids [14].

The emerging role of extracellular vesicles (EVs) in the cell communication defining them as biomarkers, has become a source of interest in the study of different metabolic disease [15-17]. For all these reasons a characterization of extracellular vesicles derived from orthobiologics of patients with different nutritional status deserves to be investigated.

2.0 Study aims and flow chart

2.1 General aim

The general purpose of this study is to evaluate the relation between the nutritional status of patients, the features of the orthobiologics products used for patients' treatment and the clinical outcomes after one-step conservative regenerative treatment for knee osteoarthritis.

2.2 Primary Outcome

The primary outcome of the study will be the identification of the proportion of responders and non-responders patients to the orthobiologic treatment (according to OMERACT-OARSI [1] criteria) at 6-month follow-up and of their related nutritional status.

For this purpose the responder or non-responder patients will be identified based on the results of the VAS, Tegner-Lysholm Activity Scale and KOOS scores according to the parameters established by Outcome Measures in Rheumatoid Arthritis Clinical Trials (OMERACT) and Osteoarthritis Research Society International (OARSI).

2.3 Secondary outcomes

The secondary outcomes of the study will be:

- the identification of the proportion of responders and non-responders patients to the orthobiologic treatment (according to OMERACT-OARSI criteria [1]) at 2 and 12-month follow-up and of their related nutritional status;

- the characterization of the orthobiologic products used for the patient's treatment.

2.4 Flow-Chart

	Enrollment	Surgical procedure	After patients discharge 2 month (+/- 2 week)	After patients discharge 6 month (+/- 2 weeks)	After patients discharge 12 month (+/- 1 month)
Sign of Informed Consent	Х				
Evaluation of inclusion criteria	Х				
Evaluation of nutritional status (anthropometric measurements, plicometry, questionnaires)		X			
Collection of PRP or microfragmented adipose tissue for orthobiologics characterization		X			
Collection of blood sample (concomitant to routine blood sample for PRR; extra routine blood sample for		X			

microfragmented adipose tissue)					
Collection of data from REGAIN questionnaires	Х		Х	Х	Х
Collection of food questionnaires		Х			

3.0 Study design

Monocentric, observational with additional procedure (extra routine blood sampling, questionnaires and measurement of Nutritional status), prospective, non-controlled.

3.1 Study methodology – subjects

After the ethics committee approval, patients meeting the inclusion criteria undergoing conservative knee regenerative medicine treatments with orthobiologics and participating to the observational study "REGAIN" will be enrolled into the study. The PROMs will be completed by patients based on their clinical condition and on the specific treatment they will receive at the REGAIN Center. The aforementioned PROMs include but are not limited to: - VAS, Tegner-Lysholm Activity Scale, KOOS.

Patients will be asked to filled the PROMs at the time of the enrollment (before the treatment) and then at 2, 6 and 12 months after the treatment.

Blood and nutritional information will be collected only the day of the treatment to allow for evaluation of the possible association between patients' characteristics and treatment outcomes. Blood sampling will be performed to carry out the following laboratory analysis, in detail: complete blood count, blood glucose, hemoglobin A1C (HbA1c), creatinine, GOT and GPT transaminases, C reactive protein, triglycerides, total cholesterol, HDL.

In particular, for patients undergoing a PRP treatment, a blood sample is already routinely harvested and therefore only an extra test tube will be added to test blood glucose, hemoglobin A1C (HbA1c), creatinine, GOT and GPT transaminases, C reactive protein, triglycerides, total cholesterol, HDL. For patients undergoing a treatment with microfragmented adipose tissue, an ad hoc blood collection will be carried out by filling two test tubes.

Nutritional information include anthropometric measurements, diet history and food consumption questionnaire (24h recall, "Quanto mangio veramente", Italian Mediterranea Index, anamnesi). Anthropometric measurements include weight and height, waist circumference, arm circumference measurements, biceps, triceps, subscapular and suprailiac folds measurement (plicometry) through the use of the skinfolder. It should be noted that the skinfolder is only one of the tools used to evaluate the patient's nutritional status, without diagnostic purposes and without the will to investigate anything about the device.

Concerning the orthobiologics characterization, PRP and microfragmented adipose tissue will undergo to different evaluations as per the observational study protocol "Utilizzo dei Patient-Reported Outcome Measures (PROMs), delle valutazioni cliniche oggettive e biomolecolari per il monitoraggio dei pazienti sottoposti a trattamenti di medicina rigenerativa".

In addition, for the purpose of this study, isolation and characterization of extracellular vesicles derived from PRP and micro fragmented adipose tissue will be performed, in order to deepen the orthobiologic characterization. The following techniques will be applied, where appropriate:

- Count and identification of cells from PRP and microfragmented adipose tissue (hemacytometer, nucleocounter, flow cytometry);
- Extracellular vesicle isolation, count and dimensional analysis (ultracentrifuge, Nanosights);
- Extracellular vesicle marker identification (flow cytometry).

These data will be analyzed for their possible association with nutritional status of the patient and clinical outcomes.

Regardless the specific protocol or investigation, the analysis will not include genomic DNA or diagnostic analysis. All samples (blood and tissues) will be analyzed at Istituto Ortopedico Galeazzi and destroyed at the end of the study.

3.2 Study duration

Total duration of study: 36 months

Starting: after approval of Ethical Committee

Time for sample collection/enrollments: 22 months

Time for data collection at the last follow-up: 12-34 months

Data analysis: 30-36 months

4.0 Patient enrollment

Will be included patients affected by knee osteoarthritis undergoing conservative regenerative medicine procedures with autologous material at IRCCS Istituto Ortopedico Galeazzi and participating to the observational study [REGAIN]

88 patients will be needed:

1) 22 subjects with body mass index (BMI) considered normal weight (≥18.5 and ≤25) undergo to Platelet-Rich Plasma (PRP) treatment;

2) 22 subjects with BMI values that exceed the normal weight range (BMI>25)

undergo to PRP treatment;

3) 22 subjects with BMI within the considered normal weight range (\geq 18.5 e \leq 25) and undergo to microfragmented adipose tissue treatment;

4) 22 subjects with BMI values that exceed the normal weight range undergo to microfragmented adipose tissue treatment. (BMI>25)

4.1 Inclusion criteria

- males and females \geq 18 and \leq 65 years;
- diagnosis of knee osteoarthritis (any Kellgren-Lawrence grade);
- indication to regenerative medicine treatments with PRP or microfragmented adipose treatment;

- participation to the observational study "REGAIN";
- patients with BMI ≥18.5;
- signature of Informed Consent for the study.

4.2 Exclusion criteria:

- Patients with BMI <18.5;
- patients who are not able to comply with the study schedule.

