5.0 Statistical methodology

5.1 Sample size

The sample size was calculated considering as primary outcome the proportion of patients not responder to treatment (according to OMERACT-OARSI [1] criteria) at the 12-month follow-up in two distinct groups of patients: subjects with body mass index within the reference ranges (Group 1 and 3) and subjects with values outside the range (Group 2 and 4). The proportion of unresponsive patients is expected to be 0.45 in Group 1 and 0.05 in Group 2. Considering a power of 80% and a significance level of 0.05 for a one-tailed Fisher exact test, the sample size is 20 subjects per group and considering 10% of possible dropouts, this number is increased to 22 patients. The study will be replicated in two classes of patients, undergoing PRP or microfragmented adipose tissue treatments. Then, 44 patients will be enrolled per class, for a total of 88 patients.

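### No minimum baseline symptom level is set and response is read from bounded scores, so patients without room to improve may count as treatment failures; the unadjusted BMI comparison should condition on baseline

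*Protocol*

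**What the plan says.** Section 4.1 requires "diagnosis of knee osteoarthritis (any Kellgren-Lawrence grade" and "indication to regenerative medicine treatments with PRP or microfragmented adipose treatment", together with an age range, REGAIN participation, BMI of at least 18.5 and consent. Section 4.2 excludes only BMI below 18.5 and "patients who are not able to comply with the study schedule". Neither section names a minimum VAS, KOOS or Tegner-Lysholm impairment.

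Section 2.2 sets the primary outcome at 6 months: "the responder or non-responder patients will be identified based on the results of the VAS, Tegner-Lysholm Activity Scale and KOOS scores", by OMERACT-OARSI criteria. No numerical threshold is written out.

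Section 5.1 compares non-response between "subjects with body mass index within the reference ranges (Group 1 and 3) and subjects with values outside the range (Group 2 and 4". It plans on these rates: "The proportion of unresponsive patients is expected to be 0.45 in Group 1 and 0.05 in Group 2". The test is a one-tailed Fisher exact test at 0.05, with 80% power and 20 evaluable patients per group, done separately for PRP and for microfragmented adipose tissue. (Section 5.1 places this at 12 months and section 2.2 at 6; the present point is the same at either time.)

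Section 5.2 compares categorical variables by chi-square or Fisher tests. It also allows two-way ANOVA or general linear regression for the effect of several variables, but names no baseline covariate. Baseline scores will exist, since section 3.1 says: "Patients will be asked to filled the PROMs at the time of the enrollment (before the treatment".

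**The concern.** VAS and KOOS have a best possible value. A patient whose baseline impairment is smaller than the improvement needed for response has no range left in which to show it. The primary analysis then counts that patient with those in whom treatment failed.

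Two consequences follow:

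- **Dilution.** If such patients are equally frequent in both BMI groups, both non-response rates rise, the contrast shrinks and power falls.
- **Bias.** If they are more frequent in one BMI group, non-response differs between the groups even when the treatment works equally well in both. The plan expects more non-response in normal-BMI patients and tests one-tailed. If those patients start with milder symptoms, the artefact runs in the tested direction. If the BMI>25 patients start milder, it works against the tested difference.

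The planning rate of 0.05 also implies that at most 1 in 20 of the BMI>25 patients can lack room to respond, and nothing in the protocol secures that.

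**Working it through.** **1. The plan's own figure.** Inputs from section 5.1: 0.45 versus 0.05, one-tailed Fisher exact test, alpha 0.05. Enumerating all outcomes gives power 0.811 at 17 per group and 0.890 at 20 per group. The stated 20 is therefore sufficient, and 0.89 is the reference for what follows.

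**2. Model.** Let f be the share of a group below the required improvement on every route to response, and q the non-response rate among the rest. Then

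observed non-response = f + (1 − f) × q.

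For the BMI>25 group, 0.05 = f + (1 − f) × q with q ≥ 0 gives f ≤ 0.05.

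**3. Equal f in both groups** (q = 0.45 versus 0.05, 20 per group):

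| f | Observed rates | Power |
|---|---|---|
| 0 | 0.450 vs 0.050 | 0.89 |
| 5% | 0.05 + 0.95 × 0.45 = 0.4775 vs 0.05 + 0.95 × 0.05 = 0.0975 | 0.80 |
| 10% | 0.10 + 0.90 × 0.45 = 0.505 vs 0.10 + 0.90 × 0.05 = 0.145 | 0.72 |

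With equal f and equal q the observed rates are identical, so no false BMI difference arises.

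**4. Unequal f: how large might it be?** The protocol gives neither the threshold nor any baseline scores, so every input here is an assumption: impairment on 0-100, SD 20, pain-function correlation 0.7, required improvement 10 or 20 points, and two routes to response (pain and function). The share below threshold on both is the bivariate normal probability that both standardised scores lie below z = (threshold − mean)/20.

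| Mean impairment | z at 20 points | f at 20 points | z at 10 points | f at 10 points |
|---|---|---|---|---|
| 50 | −1.50 | 2.8% | −2.00 | 0.7% |
| 40 | −1.00 | 8.4% | −1.50 | 2.8% |
| 35 | −0.75 | 13.3% | −1.25 | 5.0% |

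**5. False rejection.** Take q equal in both BMI groups (0.05 or 0.25, assumed), with normal-BMI patients milder. Entries are one-tailed Fisher rejection probabilities by enumeration:

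| Means (normal BMI vs BMI>25), threshold | f | q | Observed rates | 20 vs 20 | 40 vs 40 |
|---|---|---|---|---|---|
| No affected patients | 0 vs 0 | 0.05 | 0.050 vs 0.050 | 0.1% | 0.7% |
| No affected patients | 0 vs 0 | 0.25 | 0.250 vs 0.250 | 2.5% | 3.1% |
| 40 vs 50, 10 points | 2.8% vs 0.7% | 0.05 | 0.077 vs 0.057 | 0.6% | 2.8% |
| 40 vs 50, 10 points | 2.8% vs 0.7% | 0.25 | 0.271 vs 0.256 | 3.3% | 4.3% |
| 40 vs 50, 20 points | 8.4% vs 2.8% | 0.05 | 0.130 vs 0.077 | 3.5% | 10.0% |
| 40 vs 50, 20 points | 8.4% vs 2.8% | 0.25 | 0.313 vs 0.271 | 5.0% | 7.2% |
| 35 vs 50, 20 points | 13.3% vs 2.8% | 0.05 | 0.176 vs 0.077 | 10.1% | 25.7% |
| 35 vs 50, 20 points | 13.3% vs 2.8% | 0.25 | 0.349 vs 0.271 | 8.0% | 13.1% |

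The 20 versus 20 column is the comparison that section 5.1 sizes. The 40 versus 40 column applies only if the two treatment classes are pooled.

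**6. Does conditioning on baseline help?** Among patients who cannot respond, non-response is 100% in both BMI groups. That stratum contributes no BMI difference, and the remaining strata carry only patients who can respond. Stratifying on baseline therefore removes the false contrast, although it does not enable those patients to respond.

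**The case against.** The strongest case against the point is that its premise is not in the protocol. Section 2.2 cites OMERACT-OARSI and three instruments but states no minimum gain, and a third separate route to response would leave fewer patients short on all of them. Kellgren-Lawrence grade is radiographic, so admitting any grade says little about pain. Patients must have a treatment indication and be in REGAIN, whose criteria are not shown, and either may remove most near-symptom-free patients. All of this stands. It makes the size unknown, but it does not supply the missing safeguard.

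A reader might go further and infer that a false BMI finding is to be expected. The documents do not support that. A split of 16% versus 4%, for example, would give false rejection of 9% (q = 0.25) to 13% (q = 0.05) at 20 versus 20. Under the model above, however, it needs a baseline gap of roughly 0.7 SD between BMI groups, and no baseline scores by BMI are given. With a 10-point gap the false rejection stays at or below 5% at the sized comparison.

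Two other inferences also fail. One is that adjustment is useless against this problem; step 6 shows otherwise. The other is that section 4.1 must gain a symptom minimum. Broad entry is a defensible choice in an observational study nested in routine care.

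Finally, analysis detail of this kind is often left to an SAP. That is fair for the modelling specifics. The point itself rests on how the stated eligibility, endpoint and unadjusted test combine.

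**Conclusion.** The point holds in conditional form. The protocol sets no baseline symptom minimum, reads response from bounded scores, and compares proportions without naming any adjustment for baseline. If the responder rule contains a minimum absolute improvement, patients below it on every route count as treatment failures.

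Equal frequency in the BMI groups costs power: 0.89 to 0.80 at 5% and to 0.72 at 10%. Unequal frequency biases the comparison. Under the stated assumptions and a 20-point threshold, false rejection at 20 versus 20 is 3.5-5% for a 10-point baseline gap and 8-10% for a 15-point gap. If classes are pooled to 40 versus 40, it is 7-10% and 13-26%. With a 10-point threshold and a 10-point gap it stays below 5% throughout. Because the threshold, the baseline distribution and its relation to BMI are all assumed, these figures show a plausible range and do not estimate this study's error rate. The remedy is cheap enough to be worth making all the same.

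**What to change.** In section 5.2, state that:

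- the 6-month responder comparison between BMI groups conditions on enrolment VAS and KOOS, by stratification or regression adjustment;
- the number of patients whose enrolment impairment is below the required improvement on every route to response is reported for each BMI group;
- the comparison is repeated in the patients able to respond, and shown beside the all-patients result.

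The second and third items need the responder thresholds to be written down.

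**Cost.** A few sentences, using scores already collected before treatment; no new visit or measurement and no change to the entry criteria. The restricted comparison is somewhat smaller. Of 20 evaluable patients, about 20 × (1 − 0.084) = 18 remain at an 8.4% share and 20 × (1 − 0.133) = 17 at 13.3%. If the counts turn out near zero, reporting them settles the question.

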4.3 Subject identification

Researchers will prepare an identification list in chronological order of all the subjects recruited for the study to correlate an ID number with the personal information of the subjects preserving the subject anonymity, according to the D.Lgs. 196/2003 and ssm and EU Regulation 679/2016 and Guidelines of the Privacy Authority 24/07/2008.

5.0 Statistical methodology

5.1 Sample size

The sample size was calculated considering as primary outcome the proportion of patients not responder to treatment (according to OMERACT-OARSI [1] criteria) at the 12-month follow-up in two distinct groups of patients: subjects with body mass index within the reference ranges (Group 1 and 3) and subjects with values outside the range (Group 2 and 4). The proportion of unresponsive patients is expected to be 0.45 in Group 1 and 0.05 in Group 2. Considering a power of 80% and a significance level of 0.05 for a one-tailed Fisher exact test, the sample size is 20 subjects per group and considering 10% of possible dropouts, this number is increased to 22 patients. The study will be replicated in two classes of patients, undergoing PRP or microfragmented adipose tissue treatments. Then, 44 patients will be enrolled per class, for a total of 88 patients.

